6.3 Dosing and Administration

Eligible participants will be randomized to receive one of two treatment (T or R) at the ratio of 1:1 according to the randomization schedule.

Following an overnight fast of at least 10 hours, either the proposed biosimilar product (T) CHS-1420 40 mg or reference product (R) HUMIRA® 40 mg will be subcutaneously administered to participants in the right lower quadrant (left lower quadrant, if necessary, and reason for different choice of injection site should be documented) of the participants' abdomen. Participants will be dosed in a lying posture throughout the dosing procedure. Injections will be administered by a trained physician throughout the study.

Refer to the dosing manual for details of investigational products administration.

6.3.1 Trial Intervention Dose Modification

No dose modification will be expected in this single-dose PK similarity assessment trial. Here is not discussing the discontinuation of trial intervention for safety or other consideration.

6.4 Treatment of Overdose

Not Applicable.

6.5 Preparation, Handling, Storage and Accountability

6.5.1 Preparation of Trial Intervention

Sponsor should not separate out the reserve samples of the proposed biosimilar and reference products before sending the products to the research facility, and the sponsor

should package the investigational products (from the same batch) properly, so that the research facility can randomly select samples for testing and samples to be reserved as reserve samples from the same batch according to the relevant guidance ^[5]. The reserve products should be maintained in the sponsor's original container.

6.5.2 Handling and Storage of Trial Intervention

The investigational products should be stored in a locked cabinet following the storage requirements indicated in Section 6.1. The institution should properly keep all investigational products and reserve products.

For most protein therapeutics, FDA recommends that a sponsor retain the following quantities of product and dosage units, which are expected to be sufficient for evaluation by state of the art analytical methods ^[6]:

- Minimum of 10 dosage units each of the proposed biosimilar product, reference product and, if applicable, non-U.S.-licensed comparator product, depending on the amount of product within each unit; in general, this should provide for a total product mass of equal to or greater than 200 mg in a volume equal to or greater than 10 mL.

Reserve samples will be stored in locked cabinets under the required conditions in clinical research facility until at least 5 years after application approval or until at least 5 years after the completion of the trial. When the clinical research facility does not have suitable storage conditions, the reserve samples can be transferred to an independent third-party with the conditions in consistent with the requirements indicated on the label of the investigational products for storage. The reserve samples must not be returned to sponsor or any third party with interests' relationship.

6.5.3 Accountability of Trial Intervention

The staff of clinical research facility should verify the information of investigational products and sign on the receiving log after receipt of proposed biosimilar/reference products. The investigational products will be administered to all randomized participants as per the randomization code. Accurate records will be maintained regarding drug distribution, drug administration and residual drug which should be with double signature.

Distribution Plan for the Investigational Products

Investigational Products	Products name (Brand name)/Strength	Receipt	Distribution	Retention
Test/Proposed biosimilar	CHS-1420 /40 mg/0.4 mL	154 autoinjectors	119 autoinjectors	26 autoinjectors for reserve samples + 9 residual samples
Reference	HUMIRA® (Adalimumab) /40 mg/0.4 mL	154 autoinjectors	119 autoinjectors	26 autoinjectors for reserve samples + 9 residual samples

6.6 Participant Assignment, Randomization and Blinding

6.6.1 Participant Assignment

This is a single-center, randomized, single-blind, single-dose, parallel-group comparative pharmacokinetic trial in healthy adult participants.

There will be 238 healthy participants to be enrolled in the fasting trial and they will be randomized to one of two treatment groups (T, R), with an equal number of participants per treatment group.

6.6.2 Randomization

During the screening period, the screening number will be assigned to identify participants (e.g., S001). The participants will be randomized on Day -1. The stratified block randomization will be adopted. Participant random No. will be "10XX". When the randomized participant withdraws from the trial, random No. will be retained and the participant won't be enrolled again regardless of the withdrawal reason and whether a treatment has been received.

The randomization schedule will be generated by statistical department (an unblinded statistician) using SAS (Version 9.4 or higher).

6.6.3 Blinding and Unblinding

This is a single-blind trial. Only the designated clinical site personnel responsible for drug distribution and administration could reach the randomization code. The personnel and procedure should be blinded as following:

In course of the trial, sponsor staff, investigators in the clinical site and clinical research associates (other than those responsible for drug distribution and administration), statistician (other than unblinded statistician), data managers should be blinded to the treatment assignment. Staff who are responsible for drug distribution and administration

should not conduct any protocol-specified safety assessments, e.g. AE or injection site assessments post-dose.

The participants will be blinded to the assigned treatment (T or R) through the dosing process. An eye mask will be put on for participants to avoid viewing the injection.

In addition, the identity of the dosing drug will remain blinded to the bioanalytical staff during sample analysis.

Individual participant treatment assignment should be unblinded in the case of a suspected unexpected serious adverse reaction (SUSAR) that requires knowledge of the study medication received by the participant in order to interpret the event, may be essential for medical management of the participant, and may provide critical safety information about a drug that could have implications for the ongoing conduct of the trial. Otherwise unblinding is not allowed. Any blinding should be documented and dated. Treatment assignments for individual participants will remain blinded until after the study database has been cleaned and locked.

6.7 Trial Intervention Compliance

During the screening period, participants will be fully informed of the trial purpose, investigational product information, trial procedure, dosing regimen (such as dosage, administration method, period, *etc.*), clinical observation, frequency and procedure of blood collection, potential risks, compensation and indemnity to ensure the voluntary participants participation and the treatment compliance. Before dosing, the participants and the drugs to be administered should be verified carefully; After dosing, any remaining drugs, the empty package and dosing apparatus should also be checked, to record the treatment compliance.

6.8 Concomitant Therapy

Unless for treatment of AEs, any medications history of TNF- α blockers e.g. Adalimumab or its analogues (except the investigational products scheduled to be dosed in the trial) were prohibited for the enrolled participants until the last scheduled visit (including OPVs); any medication of monoclonal antibodies should not be taken within one year prior to investigational products dosing to the last scheduled visit (including OPVs); any prescription medicines or OTCs (especially antibiotics), Chinese herbal medicine or health supplementary should not be taken within 30 days prior to investigational products dosing to the last scheduled visit (including OPVs); any vaccines should not be taken within 3 months prior to investigational products dosing to 3 months after investigational products administration (including OPVs). Any medication except investigational products used during the trial (including OPVs) should be recorded in source document and case report form (CRF) in details. All the non-investigational products taken by participants during the trial (including OPVs) are treated as concomitant medications. Principal Investigator or

sponsor will determine whether the participant should continue the trial according to the interaction between investigational and non-investigational products, and whether the concomitant medication may affect the PK of the investigational products.

7 DISCONTINUATION OF TRIAL INTERVENTION AND PARTICIPANT WITHDRAWAL FROM TRIAL

7.1 Discontinuation of Trial Intervention

The participation in the clinical trial is completely voluntary. After the investigational products are distributed, the participants can withdraw from the trial for any reason without discrimination or retaliation, and their medical treatment and rights will not be affected. Participants who withdraw are not allowed to continue the trial.

7.2 Participant Withdrawal from the Trial

- 1) Determined by Investigator: The withdrawal of enrolled participants determined by the Investigator in case they are not suitable to continue in the trial.
 - A. Investigators decide that the participant should withdraw due to medical ethics;
 - B. Investigators decide that the participant should withdraw due to AEs;
 - C. Investigators decide that withdrawal is in the best interest of the participant;
 - D. The participant is of poor compliance, including but not limited to:
 - a) Failure to take the medications, blood collection and examinations as required;
 - b) Any medication or diets that affect the safety evaluation and pharmacokinetics results;
 - c) Smoking or drinking alcohol;
 - d) Other behavior which may affect the trial results.

2) Voluntary withdrawal by the participant.

Participants withdraw the informed consent officially, or won't take the investigational products or any tests any more although not withdrawing the informed consent officially, or lost to follow-up.

Handling of Withdrawals: No matter required by the participant or determined by the principal investigator, the reason for withdrawal should be fully investigated and recorded. For safety consideration, all dosed participants who withdraw from the trial should complete safety assessment.

7.3 Lost to Follow-Up

Investigators should try to contact the participant with due diligence, “lost to follow-up” will be recorded if the participant can not be contacted after at least 3 phone calls.

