11 Sampling for immunogenicity assessment: A total of four (4) blood samples for each participant will be collected for determination of serum anti-drug antibodies (ADA) / neutralizing antibodies (Nab) at 0 h (within 30 minutes pre-dose) and Day 16, Day 30, Day 65 post-dose. The actual sampling time should be recorded;

12 Participants will be discharged from the clinical research facility after PK sampling and required safety assessment at approximately 72 h after dosing while OPVs are required at approximately 96 h (Day 5), 120 h (Day 6), 144 h (Day 7), 168 h (Day 8), 216 h (Day 10), 288 h (Day 13), 360 h (Day 16), 528 h (Day 23), 696 h (Day 30), 864 h (Day 37), 1032 h (Day 44), 1200 h (Day 51), 1368 h (Day 58), 1536 h (Day 65) post-dose;

13 Safety tests will be performed at the end of trial on Day 65 for each participant before discharge from the trial, including physical examination, laboratory tests [biochemistry, hematology, urinalysis, coagulation function, serum pregnancy test (only for females)], ECG, vital signs; and also the weight of participants will be collected;

14 Any dosed participants who withdraw ahead of time should receive the scheduled safety tests for permission to discharge from the trial before leaving or at the time of the participants next scheduled follow-up visit, or any other time appropriate in discretion of investigators. In addition collection of weight will be performed.

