8.7 Pharmacokinetics

8.7.1 Pharmacokinetic Sampling

The whole blood and serum tubes should be labelled before sampling. The information on the label should include but not limit to the protocol number, randomization number, period, sampling time point, primary or backup sample.

Sample Label

Bar code CHS-1420-10 Participant: 10XX PK sample: Day X-X h-A	Bar code CHS-1420-10 Participant: 10XX PK sample: Day X-X h-B	Bar code CHS-1420-10 Participant: 10XX PK sample: Day X-X h
--	--	--

The information is as follows:

Line 1: Bar code;

Line 2: Protocol No.;

Line 3: Participant random No.;

Line 4: Indication that samples for PK analysis, and sampling day and time point (A represents the primary sample and B backup sample, both of which are serum sample tubes. It is the whole blood sample tube without A or B).

The serum drug (adalimumab) concentration will be measured and a procoagulant will be used for blood samples.

Sample Collection: A total of twenty-four (24) blood samples for each participant will be collected for determination of serum drug concentrations at 0 h (within 30 minutes pre-dose) and 2 h (Day 1), 4 h (Day 1), 8 h (Day 1), 12 h (Day 1), 24 h (Day 2), 36 h (Day 2), 48 h (Day 3), 60 h (Day 3), 72 h (Day 4), 96 h (Day 5), 120 h (Day 6), 144 h (Day 7), 168 h (Day 8), 216 h (Day 10), 288 h (Day 13), 360 h (Day 16), 528 h (Day 23), 696 h (Day 30), 864 h (Day 37), 1032 h (Day 44), 1200 h (Day 51), 1368 h (Day 58), 1536 h (Day 65) post-dose. Approximately 3.5 mL of blood will be collected into vacutainer tubes containing the procoagulant followed by gentle inversions to get mixed up and then be left standing still till coagulation. If blood samples are obtained from an indwelling catheter rather than straight venipuncture, withdraw approximately 1 mL blood prior to obtaining the PK blood sample each time. After each blood collection, use an appropriate amount of

normal saline solution to seal the catheter.

Pre-handling of Samples: The coagulated blood samples will be centrifuged in a refrigerated centrifugue at 2-8°C. Serum will be transferred into two tubes – tube “A” for the primary assay sample and tube “B” as the backup sample. Serum will be stored in a freezer at -70°C (temperature range -90°C ~ -60°C) until shipment to the bioanalytical laboratory for analysis.

Refer to the sampling manual for detailed requirements regarding sample processing.

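### A dosed participant recorded as lost to follow-up counts as withdrawn and has no stated route back to PK or antibody sampling, even if consent stands and contact is regained

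*Protocol*

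**What the plan says.** Protocol 7.3, repeated in the synopsis under the withdrawal criteria, has two parts. It sets an effort standard, "Investigators should try to contact the participant with due diligence", and a trigger: the status "will be recorded if the participant can not be contacted after at least 3 phone calls". Due diligence is not defined, and no interval between calls or second contact route is given.

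Protocol 7.2 item 2 defines voluntary withdrawal. Besides formal withdrawal of consent, it takes in people who stop "although not withdrawing the informed consent officially, or lost to follow-up".

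Protocol 7.1 states the consequence: "Participants who withdraw are not allowed to continue the trial". Section 6.6.2 adds that after withdrawal "the participant won't be enrolled again regardless of the withdrawal reason and whether a treatment has been received".

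For those already dosed, 7.2 asks that safety assessment be completed. Footnote 14 to the Schedule of Activities (1.3) says: "Any dosed participants who withdraw ahead of time should receive the scheduled safety tests for permission to discharge from the trial before leaving". It also allows those tests "at the time of the participants next scheduled follow-up visit" or at another time the investigator finds suitable, and adds body weight. It names no PK or ADA/Nab sample.

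**The concern.** This is a single-dose trial. Once the injection has been given there is no treatment left to stop, and every outpatient visit is sampling and safety follow-up. There are 14 such visits up to Day 65, and healthy volunteers can be expected to miss some of them and be hard to reach for a time.

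Loss of contact and withdrawal of consent differ in kind. The first may end by itself; the second is a decision that must be respected. By putting them in one category and attaching a bar on continuing, the protocol discards data that a willing participant could still provide. The late samples carry most weight here. They determine the terminal slope, and so Kel and AUC0-∞, and they include the later antibody results on which the immunogenicity comparison relies. The wording would even allow a returning participant to have safety blood drawn at a scheduled visit with no PK tube taken.

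**Working it through.** **The sections side by side**

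1. Trigger (7.3): due diligence, and at least three failed calls.
2. Classification (7.2 item 2): lost to follow-up is a form of voluntary withdrawal, with or without formal withdrawal of consent.
3. Consequence (7.1): withdrawn participants may not continue.
4. What remains (7.2 and footnote 14): safety tests and weight.
5. Route back: neither the protocol nor the SAP says that a participant recorded as lost and later reached may resume sampling.

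Section 6.6.2 is not needed for this chain. Section 14.2 defines enrollment as randomization, so 6.6.2 can be read as barring only a second randomization.

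**Samples at stake**

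Protocol 8.7.1 plans 24 PK samples per participant: "A total of twenty-four (24) blood samples for each participant will be collected for determination of serum drug concentrations". Section 8.10 plans 4 immunogenicity samples (0 h, Day 16, Day 30, Day 65). Take a participant who attends Day 16 (360 h), misses Day 23 (528 h) and is then recorded as lost:

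- PK samples already taken, 0 to 360 h: 17.
- PK sample missed in any case, 528 h: 1.
- PK samples forfeited by the status: 696, 864, 1032, 1200, 1368 and 1536 h = 6.
- Check: 17 + 1 + 6 = 24.
- Post-dose ADA/Nab samples forfeited: Day 30 and Day 65 = 2 of 3.

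Samples still due at other points where contact may end, counting the first missed visit:

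| Last visit attended | PK still due | ADA/Nab still due |
|---|---|---|
| Day 4 discharge | 14 of 24 | 3 of 4 |
| Day 16 | 7 of 24 | 2 of 4 |
| Day 30 | 5 of 24 | 1 of 4 |

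**Consequence for AUC0-∞**

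Protocol 9.2.1.1 defines AUC0-∞ = AUC0-t + Ct/Kel. Section 4.2 gives a half-life of about 2 weeks, or 336 h. Assuming one-compartment elimination, the share of AUC beyond the last sample at time t is at least 2^(−t/336), and slow absorption only raises it:

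- Sampling ends at 360 h: 2^(−360/336) = 0.48.
- One missed visit, then sampling to 1536 h: 2^(−1536/336) = 0.04.

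So at least about 48% of the area would be extrapolated when the participant is closed out, against about 4% when sampling resumes. This illustrates the mechanism and is not a prediction. Neither document limits the extrapolated share, and the Pharmacokinetic Similarity Set needs only one evaluable parameter. Such a profile could therefore enter the primary analysis with a weak AUC0-∞, or contribute Cmax alone.

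**Sample size**

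The planned 238 reproduces. With CV 44%, σ = √ln(1 + 0.44²) = 0.421. At GMR 1.05, limits 0.80 to 1.25 and one-sided α 0.05, power with 101 per arm is 89.99%, and 202/0.85 = 237.6, which rounds up to 238. The allowance is thus 238 − 202 = 36 participants for drop-out of every kind. The documents do not say how many of these would be losses of contact, or how many of those would return, so no change in power can be derived.

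**The case against.** The strongest reply is that the bar on return is an inference. Section 7.3 does not say that the status is final. The sentence in 7.1 follows text about participants who choose to leave, and 9.2.3 (SAP 4.3) already treats a missing sample between two quantifiable ones as null, so the plan expects people to miss a visit and come back. A careful site might simply resume sampling.

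Part of this stands. Nothing says the status cannot be reversed, and a missed visit alone does not trigger it. But 7.2 defines the term that 7.1 uses, so the joined reading is the natural one at the site. The missing-data rule helps only participants who were never recorded as lost.

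Three stronger readings are tempting and should be resisted:

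- A reader might infer that one missed contact is enough. The text requires due diligence and at least three failed calls, and three is a floor. The missing call interval is missing detail and does not carry the point.
- A reader might infer that the rule removes the end-of-trial safety tests. Section 7.2 and footnote 14 still provide safety tests for a dosed participant who reappears.
- A reader might infer a loss of power. Drop-out of about 15% is already planned for, earlier samples stay in the analysis sets, and any assumed share of returning participants would have no basis in the documents.

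One limit remains: the early-withdrawal column of the Schedule of Activities table was not readable in the text available to me. If it provides for a PK or ADA/Nab sample at that visit, the forfeited samples fall by that amount. Hence the words up to 6.

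**Conclusion.** The point holds as a fault in the follow-up rules. Sections 7.1, 7.2 and 7.3 together turn a recoverable loss of contact into withdrawal and provide no way back to PK or ADA/Nab sampling for a dosed participant whose consent stands.

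The size is per participant: up to 6 PK and 2 post-dose ADA/Nab samples in the Day 23 example, with AUC0-∞ becoming largely extrapolated or not estimable. Cmax is kept if the peak had already been sampled. How often this would happen is unknown. The conclusion rests on reading 7.1 and 7.2 together and on footnote 14 being the full list of what a withdrawn participant receives. The change is worth making because it protects primary-endpoint and immunogenicity data at almost no cost.

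**What to change.** - **7.2 and the synopsis:** take lost to follow-up out of the definition of voluntary withdrawal and give it its own category.
- **7.1 and 7.3:** state that a dosed participant who has not withdrawn consent and is reached again before Day 65 resumes the remaining scheduled PK, ADA/Nab and safety assessments. State also that contact is attempted again at each later scheduled visit.
- **14.2 and footnote 14:** align the definition of early withdrawal and the list of assessments with the above. Check the early-withdrawal column of the Schedule of Activities against them.
- **Related wording:** say that resuming is not re-enrollment under 6.6.2. Make clear how the investigator's option in 7.2 to withdraw someone for missed blood collection applies to a participant who returns; otherwise that option could undo the change.

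A minimum spread of days between calls, or recording the status only at the close of Day 65, would be reasonable additions but are optional.

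The cost is protocol wording, a few more phone calls and some profiles with an interior gap, which 9.2.3 already handles. No new procedure is added.

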7.4 Trial Stopping Rules

Not Applicable.

8 TRIAL ASSESSMENTS AND PROCEDURES

8.1 Screening/Baseline Assessments and Procedures

Healthy males and females of age 18 – 55 years old inclusive will be enrolled. After providing written informed consent, participants will undergo a complete collection of data within 28 days prior to investigational products dosing including:

- Demographic data (including gender, age, height, weight, BMI, nation, and race, *etc*).
- Medical /surgical history, allergy history, medication history, drug abuse history, history of tobacco and alcohol.
- Chest X-ray.
- Physical examination (detailed in [Section 8.3.1](#))
- Vital signs (detailed in [Section 8.3.2](#))
- ECG (detailed in [Section 8.3.3](#))
- Clinical laboratory tests [biochemistry, hematology, urinalysis, coagulation function, antinuclear antibody, viral tests (HBV, HCV, HIV, syphilis, tuberculosis) and a serum pregnancy test (females only), see [Section 13.2](#)].
- A urine drug abuse test (Morphine, Methamphetamine, Ketamine, Tetrahydrocannabinol and Methylenedioxymethamphetamine in urine) and alcohol breath test.

Viral tests results obtained within the previous 3 months prior to investigational products dosing may be used instead of obtaining these tests at the screening visit. Among them, the urine drug abuse test and alcohol breath test will be conducted before check-in (Day -1) and retested upon OPVs on Day 30.

